**Insulin Only Bionic Pancreas
Bridging Trial
Adult RCT Phase**

Statistical Analyses Plan

Version 0.4

September 21, 2018

Based on Protocol Version 8.0

Note: The table shells are included in a separate document

1 **Version History**

2

Version	Author	Approvers	Effective Date	Revision Description	Study Stage
1.0	[name]/ [name]	[name] [name] [name] [name]	9/xx/2018	Original Version	The Adult RCT Phase started the enrollment on 7/xx/2018. Still enrolling

3

4 **Lead Statistician and Author:**

5 _____

6

7 **Senior Statistician Approver:**

8 _____

9

10 **JAEB PI Approver:**

11 _____

12

13 **Sponsor Approver:**

14 _____

15

16 **Study PI Approver:**

17 _____

18

19 **1. Study Overview**

20 This document outlines the statistical analyses to be performed for the IOBP Bridging Trial – Adult RCT
21 Period - to be presented to DSMB and maybe published.

22
23 The IOBP Bridging Trial consists of four different periods in this order:

- 24 - Test Run,
- 25 - Adult RCT,
- 26 - Pediatric Transitional,
- 27 - Pediatric RCT.

28
29 The Test-Run Period will be completed and the data will be reviewed to verify safety prior to beginning
30 the Adult RCT Period.

31
32 The Adult RCT Period will consist of a multi-center, three-period, random-order, cross-over, feasibility
33 study in 36 adult participants ≥ 18 years old with T1D (18 participants at MGH and 18 participants at
34 Stanford). All 18 adult participants at MGH will have a Senseonics Eversense CGM sensor implanted prior
35 to the initiation of the Adult RCT Period by the clinical PI at MGH ([name]) or by a study
36 physician under his supervision. These subjects will use the Senseonics Eversense CGM as the input to the
37 bionic pancreas instead of the Dexcom G5. All 18 adult participants at Stanford will use the Dexcom G5
38 CGM as the input to the bionic pancreas. All other aspects will remain the same across the two sites.

39 Insulin therapy for each participant will be administered (i) in one period using the iLet in the insulin-only
40 configuration with the iLet pigtail adapter and the iLet ready-to-fill insulin cartridge, the Contact Detach
41 infusion set, and the insulin analog that they use for their usual care (either Humalog or Novolog), (ii) in
42 another period using the iLet in the insulin-only configuration using the iLet pigtail adapter, the Contact
43 Detach infusion set, and faster insulin aspart (Fiasp) in PumpCart, where the pharmacokinetic (PK)
44 parameter for tmax used by the insulin-dosing algorithm will be set to the same value as is used for Humalog
45 and Novolog (65 minutes), and (iii) in a third period using the participant's own usual care (UC), where
46 each participant will wear a CGM. All three experimental periods will be followed by round-the-clock,
47 remote, telemetric monitoring for hyperglycemia (> 300 mg/dl for ≥ 90 minutes) and hypoglycemia (< 50
48 mg/dl for ≥ 15 minutes). The three experimental periods will each have a duration of 7 days. Washout
49 periods of approximately 7 days in duration will follow the first and second experimental periods. The
50 washout period could be as short as 5 days or as long as 9 days, depending on scheduling of study visits.
51 Of the 36 participants, 9 at MGH and 9 at Stanford will use MDI therapy for their usual diabetes
52 management; the remaining 18 will use insulin pump therapy. The participants at Stanford will wear the
53 Dexcom G5 CGM and the participants at MGH will wear the Senseonics Eversense CGM. This will allow
54 us to collect further comparative accuracy data on both the Senseonics Eversense and the Dexcom G5 in
55 the outpatient setting using the Ascensia Contour Next One meter as the reference. Four participants at
56 MGH will have a Senseonics Eversense CGM sensor implanted and will participate in a 3-day supervised
57 Test Run. This Senseonics Eversense Test Run Period will be completed and data will be reviewed to verify
58 safety prior to beginning the Adult RCT Period at MGH using the Senseonics Eversense CGM sensor as
59 the input to the iLet. The cohort of 18 participants at MGH and 18 participants at Stanford might run
60 simultaneously, might overlap, or might not overlap in time.

61

62 Major eligibility criteria include:

- 63 • Clinical diagnosis of type 1 diabetes for at least 12 months
- 64 • HbA1c level < 11.0%
 - 65 ○ At least 13 participants must have an HbA1c level of 8–11%
 - 66 ○ At least 13 participants must have an HbA1c level < 8%
- 67 • Using an FDA-approved insulin therapy (including Fiasp on MDI therapy for adults, Humalog or
68 Novolog with CSII or MDI therapy; glulisine users will be excluded)
 - 69 ○ 18 participants must use MDI therapy to manage their diabetes
 - 70 ○ 18 participants must use CSII therapy to manage their diabetes
- 71 • Age \geq 18 years old
 - 72 ○ Approximately 9 participants in a young adult group (18–24 years old)
 - 73 ○ Approximately 27 participants in an adult group (\geq 25 years old)
- 74 • At least 3 daily SMBG or 2 if used with a CGM

75

76 The following table gives an overview of the schedule of study visits and key procedures during each one
 77 of the three 7-day randomized treatment periods [BP with analog insulin (1), BP with rapid insulin (2),
 78 and UC (3)]:

	Screening	Senseonics Eversense Sensor Insertion	Each Treatment Period			Senseonics Eversense Sensor Removal
			0	Day 3 or Day 4	Day 7	
Informed Consent	X					
Eligibility assessment	X		X			
Bloodwork: eGFR and HbA1c	X					
EKG	X					
Body weight	X		X		X	
Urine pregnancy test	X					
Physical exam	X					
Insertion of Dexcom CGM sensor			X			
Insertion of Senseonics Eversense CGM sensor		X				
Removal of Senseonics Eversense CGM sensor						X
Psychosocial questionnaires			X		X	
Data download					X	
Adverse event querying			X	X	X	

79

80 **2. Statistical Hypotheses**

81 The primary outcome for this study is CGM-measured mean glucose when compared during (2) BP with
82 rapid insulin and UC (3) treatment periods.

83 The hypotheses are:

- 84 1. *Null Hypothesis*: There is no difference in mean CGM-measured glucose during UC and BP with
85 rapid insulin treatment periods
- 86 2. *Alternative Hypothesis*: The mean CGM-measured glucose is different during UC and BP with
87 rapid insulin treatment periods.

88

89 The intervention will be considered effective if the above null hypothesis is rejected using a significance
90 level of 0.05 (i.e. $p < 0.05$).

91

92 **3. Sample Size**

93 Thirty-six subjects will be enrolled and randomized at two sites. This is a convenience sample; however
94 assuming an effective SD of 25 mg/dl for mean glucose, the half width of the associated 95% confidence
95 interval are approximately ± 10 mg/dl for $N=36$ and ± 15 mg/dl for $N=18$. Results from the control period
96 of the JDRF CGM RCT were used to estimate SD for mean glucose in the proposed study.

97

98 **4. Outcome Measures**

99 **4.1 Primary Efficacy Outcome**

- 100 • CGM-measured mean glucose

101

102 **4.2 Secondary Efficacy Outcome**

103

104 **4.2.1 Secondary Efficacy Endpoint Included in Hierarchical Analysis**

- 105 • CGM-measured time < 54 mg/dl

106

107 **4.2.2 Other Secondary Efficacy Outcomes**

108 The following endpoints are considered exploratory.

- 109 • CGM metrics related to hypoglycemia
 - 110 ○ % < 70 mg/dL
 - 111 ○ % < 60 mg/dL
 - 112 ○ low blood glucose index
- 113 • CGM metrics related to overall control
 - 114 ○ % time in target range 70-180 mg/dL
 - 115 ○ % time in target range 70-120 mg/dL
 - 116 ○ glucose variability measured with CV (coefficient of variation)
 - 117 ○ glucose variability measured with MODD (mean of daily difference)
- 118 • CGM metrics related to hyperglycemia
 - 119 ○ % > 180 mg/dL
 - 120 ○ % > 250 mg/dL
 - 121 ○ high blood glucose index

122
123
124
125
126
127

- Total daily dose of insulin
- Questionnaires - The following table provides a description of the questionnaires to be administered during each one of the three 7-day randomized treatment periods [BP with analog insulin (1), BP with rapid insulin (2), and UC (3)]:

Questionnaire's Name	Day 0	Day 7	Description
Diabetes Treatment Satisfaction Questionnaire - Status	X		Measures patient satisfaction with diabetes treatment. 8 items (6 for assessing treatment satisfaction and two for frequency of hypoglycemia and hyperglycemia). Scale 0-6. Higher scores denote higher satisfaction or higher frequency of hypoglycemia/hyperglycemia.
Diabetes Treatment Satisfaction Questionnaire - Change		X	Similar with the above (Status); except scale -3 to 3.
Diabetes Distress Scale	X	X	Measures Adult and Partner of Adult diabetes distress. Adult: 17 items (4 subscales and total score) and scale 1-6. Partner: 21 items (4 subscales and total score) and scale 0-4. Higher score denotes more of a problem or more distress.
Hypoglycemia Fear Survey	X	X	23 items (2 subscales and total score). Scale 0-4. Higher score denotes more fear.
Hypoglycemia Confidence Scale - Status	X	X	Measures confidence status. 8 items and a 4-level scale.
Hypoglycemia Confidence Scale - Change		X	Measures confidence change. 8 items and a 5-level scale.
INSPIRE Survey	X	X	Measures experience with automated insulin delivery systems. Adult and partner versions. 31 items. 5-point Likert scale.
Bionic Pancreas User Opinion Survey*		X	Measures user's experience with BP. 43 items. Two subscales (benefits and difficulties) and total score. 5-point Likert scale.
Daily At-Home Questionnaires			Administered at the end of each day – expected 6 times for each subject and randomized period combination. 17 items – most of them with sub-items (depending on the subject's answer).

128 *to be administered only during the two BP periods

129 **4.3 Calculation of CGM Metrics:**

- 130
- All sensor data excluding the first 48 hours will be included in the calculation of glycemic metrics.
 - Only subjects with at least 24hr of CGM data in any two of the three treatments periods will be included in CGM analyses. It is considered that 24hr of data is the minimum and a representative amount of data for any treatment period.
 - If there are 12-<24hr of CGM data from days 3-7 in each one of the three treatment periods and there are more CGM data during days 1-2, then the data from days 3-7 will be supplemented with
- 136

- 137 data from days 1-2 (going backwards) until 24hr of data is reached. Otherwise the data are
138 considered missing for that treatment period.
- 139 • Metrics will be calculated giving equal weight to each CGM point from each treatment period.
- 140

141 **5. Description of Statistical Methods**

142 **5.1. General Approach**

143 Analyses will involve pairwise comparisons of the three treatment arms:

- 144 1. Bionic Pancreas (BP) with analog insulin
 - 145 2. Bionic Pancreas (BP) with rapid insulin
 - 146 3. Usual Care (UC)
- 147

148 All primary, hierarchical, and secondary analyses comparing the three treatment periods will follow the
149 intention-to-treat (ITT) principle with each period analyzed according to the treatment assigned by
150 randomization. All randomized participants with at least 24hr of CGM readings during at least two of the
151 three treatment periods will be included in the primary, hierarchical, and secondary analyses of CGM
152 metrics. There will be no imputation of missing data.

153 All p-values will be two-sided.

154 Standard residual diagnostics will be performed for all analyses. If values are highly skewed, then a rank
155 transformation will be used instead for the primary and secondary outcomes. From prior experience, the
156 values for time <54 mg/dl will have a skewed distribution and for mean glucose a bell-shaped
157 distribution.

158

159 **5.2. Analyses Cohorts**

160 Primary and Secondary Analyses:

- 161 • For CGM-based and insulin outcomes, all randomized participants and treatment periods will be
162 analyzed according to the ITT principle and the 24hr rule as described above.
 - 163 • For questionnaires, all questionnaires with at least one item answered will be included in
164 analyses. Total and subscale score may be calculated or not depending on specific instructions or
165 rules (see section 7.2).
- 166

167 Safety Analyses:

- 168 • Safety outcomes will be reported for all enrolled participants, irrespective of whether the safety
169 event happened during the randomized treatment periods or in between (i.e. during wash-out
170 periods).
- 171

172 Sensitivity Analyses:

- 173 • Primary and secondary CGM-based outcomes will be replicated using:
 - 174 ○ all CGM data during the randomized treatment periods (i.e. days 1-7), and
 - 175 ○ only the first 24hr of CGM data from each treatment period following randomization.
 - 176 • Additional models for primary and secondary outcomes will be run to test for any carry-over
177 effects, by adding a treatment by order interaction term.
- 178

179

180 **6. Primary Analysis**

181 The primary analysis will be a comparison of CGM-measured mean glucose between (2) BP with rapid
182 insulin versus (3) UC treatment periods.

183

184 Plots and summary statistics appropriate to the distribution for mean glucose will be reported.

185

186 A repeated measures linear model with mean glucose as the dependent variable will be fit to the data
187 including all three treatment periods. The model will adjust for treatment period and account for
188 correlated data from the same subject using an unstructured covariance matrix.

189

190 The p-value for the primary analysis will be calculated using a contrast in the model described above
191 between the (2) BP with rapid insulin (3) UC treatment arms. From prior experience, the values for mean
192 glucose will follow a bell-shaped distribution. Residual values will be examined for an approximate normal
193 distribution. If values are highly skewed then rank transformation will be used instead.

194

195 **7. Secondary Analyses**

196 Plots and summary statistics appropriate to the distribution will be given for both mean glucose and time
197 below 54 mg/dl for all three treatment arms.

198

199 For mean glucose, contrasts from the same model described above will also be used to compare:

- 200 • (2) BP with analog insulin versus (3) UC, and
- 201 • (2) BP with rapid versus (1) BP with analog insulin

202 Both of these are considered secondary analyses.

203

204 A similar model will be fit with time below 54 mg/dl as the dependent variable with contrasts for all
205 three pairwise comparisons of the treatment arms. It is anticipated that the distribution of this metric will
206 be skewed. In this case, a transformation will be used as described above.

207

208 **7.1 Hierarchical Analyses**

209 To preserve the overall type 1 error for the 6 comparisons (2 selected key secondary endpoints times 3
210 treatment arm pairs), a hierarchical testing procedure will be used. If the primary analysis described above
211 results in a statistically significant outcome ($p < 0.05$), then testing will proceed to the next comparison in
212 the following order:

- 213 • Mean glucose for (2) BP with rapid insulin vs. (3) UC (primary analysis)
- 214 • Time <54 mg/dl for (2) BP with rapid insulin vs. (3) UC
- 215 • Mean glucose for (1) BP with analog insulin vs. (3) UC
- 216 • Time <54 mg/dl for (1) BP with analog insulin vs. (3) UC
- 217 • Mean glucose for (2) BP with rapid vs. (1) BP with analog insulin
- 218 • Time <54 mg/dl for (2) BP with rapid vs. (1) BP with analog insulin

219

220 This process continues iteratively moving to the next variable down on the list until a non-significant
221 result ($p \geq 0.05$) is observed, or all six comparisons have been tested. If a non-significant result is

\\cifs2\[name]\$\gen 3 ilet iobs\protocol\iobp bridging adult rct sap v0.4 9_21_2018.docx

Printed: 7/16/2019 11:36 AM

Page 9 of 14

222 encountered, then formal statistical hypothesis testing is terminated and any comparisons below on the list
 223 are not formally tested.

224 For example, in the hypothetical scenario depicted in the table below, the first three comparisons both
 225 have a significant result so testing continues to the fourth row [Time <54 mg/dl for (1) BP with analog
 226 insulin vs. (3) UC]. The result is not significant for that fourth row (p = 0.06) so testing stops. No formal
 227 hypothesis test is conducted for the fifth and sixth comparisons on the list in this example scenario.

228

229 **Table 1. Example application of the hierarchical procedure to control type 1 error.**

HIERARCHICAL ORDER	COMPARISON	CONTRAST P-VALUE	SIGNIFICANT?	ACTION
1 st	Mean glucose for (2) BP with rapid insulin vs. (3) UC (primary outcome)	0.001	Yes	Test next comparison
2 nd	Time <54 mg/dl for (2) BP with rapid insulin vs. (3) UC	0.02	Yes	Test next comparison
3 rd	Mean glucose for (1) BP with analog insulin vs. (3) UC	0.007	Yes	Test next comparison
4 th	Time <54 mg/dl for (1) BP with analog insulin vs. (3) UC	0.06	No	Stop formal testing
5 th	Mean glucose for (2) BP with rapid vs. (1) BP with analog insulin	Not tested	Unknown	N/A
6 th	Time <54 mg/dl for (2) BP with rapid vs. (1) BP with analog insulin	Not tested	Unknown	N/A

230

231 Regardless of the results of the hierarchical testing, summary statistics appropriate to the distribution will
 232 be tabulated.

233

234 **7.2 Other Endpoint Analyses**

235 CGM-Measured Outcomes

236 The analyses for the secondary CGM-measured outcomes will parallel the descriptive statistics and
 237 regression model mentioned above for the primary outcome without the hierarchical procedure.

238 Analyses will also be done limiting to daytime (6am-12mn) and nighttime (12mn-6am) data. Only
 239 subjects with at least 12hr of CGM data in any two of the three treatments periods will be included in
 240 daytime/nighttime CGM analyses.

241

242 Questionnaires

243 For each question, the percent of all answers will be reported across all subjects by treatment periods; and
244 if applicable, by beginning and ending of each treatment period. For questions with additional numeric or
245 ordinal scales, mean score will be reported in addition to the percent.

246
247 Some questionnaires will be administered at the beginning and ending of each treatment period, and the
248 results presented as such. If a subject completed the beginning but not the ending questionnaires, the
249 results will be presented as such (i.e. with different underlying number of subjects).

250
251 For some questionnaires total and subscale scores will be calculated and mean \pm SD values or percentiles
252 appropriate to the distribution will be reported across all subjects by treatment periods.

253
254 All questionnaires will be administered online (through REDCap) and subjects can skip specific
255 questionnaires or questions within a questionnaire. All questionnaires will be scored according to the
256 instructions given in the manual. In case no manual exists for a given questionnaire or the manual does
257 not provide guidance on how to handle missing questions, then the following “75% rule” will be used.
258 For all questionnaires, at least 75% of the questions must be completed to be included in the
259 analysis. This 75% rule will be applied separately for the total score and each subscale so it is possible
260 the sample size will be different for some subscales. The score used for analysis will be based on the
261 average among the questions that were answered and then scaled accordingly in order to a corresponding
262 total or subscale score.

263
264 The Daily At-Home Questionnaire will be administered at the end of each day (for a maximum of 6 times
265 for each one of the three treatment periods). Each question in this questionnaire will be first summarized
266 (percent or mean) and presented at period level and then summarized across all subjects by treatment
267 period as mentioned above.

268
269 No formal hypothesis tests will be done for questionnaires.

270 271 Sensor Accuracy

272 Each reference glucose measurement from the blood glucose meter will be paired with the closest sensor
273 reading within \pm 5 minutes (choosing the CGM that immediately precedes the BGM value, rather than the
274 other way around). Each reference measurement will be paired with only reading from sensor and each
275 sensor reading will only be paired with one meter reference value. Any meter measurements used to
276 calibrate the sensor will be excluded from the accuracy analysis. Any data available during the wash-out
277 periods will also be included.

278
279 Difference, absolute relative difference, and International Organization for Standardization criteria (ISO)
280 will be calculated for each sensor-reference pair. Descriptive summary statistics will be reported separately
281 for Eversence and DexCom according to their distribution overall and by different meter ranges:

- 282 • <70 mg/dl
- 283 • 70-180 mg/dl
- 284 • >180 mg/dl
- 285 • >250 mg/dl

286

287 Insulin Outcomes
288 Total daily insulin analyses during the BP treatment period will include data from days 3-7 (i.e. exclude
289 the first 48 hours of data) and will be displayed using boxplots for each day. Summary statistics for the
290 total daily insulin reported on the CRF on Days 0 and 7 will also be given for both treatment periods.
291

292 **8. Safety Analyses**

293 All subjects will be included in these analyses and all their safety events will be reported.
294 The circumstances of all reportable cases of the following will be summarized and tabulated by
295 randomized treatment periods and wash-out intervals:

- 296 • Severe hypoglycemia (as defined in Section 8.1 of the protocol)
- 297 • Diabetic ketoacidosis (as defined in Section 8.1 of the protocol)
- 298 • All other adverse events
- 299 • Ketone events defined as ketone level >1.0 mmol/l
- 300 • CGM-measured hypo- and hyperglycemia events

301
302 Due to the relatively short follow-up duration for this study, it is unlikely there will be enough such
303 events for a formal statistical comparison. However, if there are enough events, a Poisson regression that
304 accounts for correlated data from the same subject will be used to compare the number of events between
305 the three treatment periods. The amount of follow up will be included as an offset covariate to compare
306 the rates. Influence diagnostics will be reviewed and if outliers are present then the model will be run
307 without them and the results compared.

308
309 The CGM-measured (days 1-7) hypo- and hyperglycemia events will use all available CGM data and are
310 defined as follows:

- 311 • hypoglycemia - defined as at least 15 consecutive minutes <50 mg/dl
- 312 • hyperglycemia - defined as at least 90 consecutive minutes >300 mg/dl

313

314 **9. Intervention Adherence**

315 A listing of the following outcomes as well as summary statistics appropriate to the distribution will be
316 given to assess intervention adherence for the study:

- 317 • The daily frequency of downloaded SMBG use
- 318 • BP use (using days 3-7 and days 1-7), # hours BP was “on”, # hours BP was in Closed Loop
319 mode and % of time BP was in Closed Loop mode.

320

321 **10. Adherence and Retention Analyses**

322 The following tabulations and analyses will be performed by treatment period to assess protocol
323 adherence for the study:

- 324 • Flow chart accounting for all subjects at all scheduled visits
- 325 • A listing of protocol deviations
- 326 • A listing of unscheduled visits
- 327 • A listing of subjects who dropped out of the study and reasons

328

329 **11. Baseline Descriptive Statistics**

330 Baseline demographic and clinical characteristics of all participants will be summarized in a table using
331 summary statistics appropriate to the distribution of each variable. Descriptive statistics will be displayed
332 overall and will include:

- 333 • Age
- 334 • HbA1c
- 335 • Gender
- 336 • Race/ethnicity
- 337 • Income, education, and insurance status
- 338 • Clinical Center
- 339 • Diabetes duration
- 340 • BMI
- 341 • Total daily insulin
- 342 • Previous Pump and CGM use

343

344 **12. Device Issues**

345 Device issues reported on the CRF by the sites will be tabulated according to treatment period.

346 **13. Planned Interim Analyses**

347 No formal interim analyses are planned for this study.

348 The DSMB will review data collected.

349

350 **14. Subgroup Analyses**

351 This study was not powered for subgroup analyses. These are considered exploratory and results will be
352 interpreted with caution. Subgroup analyses will only be performed for those pairwise treatment
353 comparisons (see above) that were statistically significant at $p < 0.05$.

354

355 These analyses will include, but will not be limited to, evaluating potential differences between sites,
356 including differences between the RCT Period at the MGH site using the Senseonics Eversense as the
357 input to the iLet and the RCT Period at the Stanford site using the Dexcom G5 CGM as the input to the
358 iLet. The general approach for these analyses will be to add an interaction term for the subgroup factor by
359 treatment into the models used for the analyses described above. Continuous variables will be modelled as
360 such in the subgroup analyses to calculate p-values for interaction, but summary statistics will be
361 displayed as discrete subgroups in tables.

362

363 Summary statistics appropriate to the distribution will be tabulated in each subgroup by treatment period.

364

365 The following baseline factors will be assessed:

- 366 • Age

- 367 • Baseline HbA1c
- 368 • Study Center/Sensor
- 369 • Insulin method: pump versus injection
- 370 • T1D duration

371

372 **15. Multiple Comparison/Multiplicity**

373 For the 6 key comparisons listed in Section 7.1, strong control of the familywise error rate (FWER) will
374 be accomplished using the hierarchical procedure described above.

375

376 For all other secondary analyses which are considered exploratory, the false discovery rate will be
377 controlled using the adaptive Benjamini-Hochberg procedure. The method will be applied separately for
378 the following four categories:

- 379 • Secondary CGM-measured and insulin for BP-rapid vs. UC comparisons,
- 380 • Secondary CGM-measured and insulin for BP-analog vs. UC comparisons,
- 381 • Secondary CGM-measured and insulin for BP-rapid vs. BP-analog comparisons, Subgroup
382 analyses mentioned in section 14 (if applicable)

383 No multiple comparisons adjustment will be made for sensitivity analyses or safety analyses.

384

385 **16. Additional Analyses**

386 Twenty-four hour boxplots by the three treatment periods will be generated for the following CGM-based
387 outcomes:

- 388 • % <54 mg/dl
- 389 • Mean glucose
- 390 • % >180 mg/dl
- 391 • % 70-180 mg/dl
- 392 • Coefficient of variation

393

394 The purpose of the above boxplots will be to see the trend of each outcome within a 24-hour day for each
395 treatment period and across all subjects.

396

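### SAP Section 2 defines effectiveness as any two-sided rejection, so a significant rise in mean glucose on the bionic pancreas with rapid insulin would also qualify

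*SAP*

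**What the plan says.** SAP Section 2 gives the primary comparison as mean CGM glucose on BP-rapid against UC. The null is no difference. The alternative carries no direction: "The mean CGM-measured glucose is different during UC and BP with" rapid insulin. The decision rule follows at once: "The intervention will be considered effective if the above null hypothesis is rejected using a significance" level of 0.05.

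The other places where a direction could have been given do not give one:

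- Section 4.1 names the outcome only.
- Section 5.1: "All p-values will be two-sided".
- Section 6: "The primary analysis will be a comparison of CGM-measured mean glucose between (2) BP with rapid" insulin and UC. On the test it says "The p-value for the primary analysis will be calculated using a contrast in the model described above", with a fallback: "If values are highly skewed then rank transformation will be used instead".
- Section 7.1: if the primary p-value is below 0.05, "then testing will proceed to the next comparison in" the listed order. It also says "Regardless of the results of the hierarchical testing, summary statistics appropriate to the distribution will" be tabulated, but does not link those statistics to the verdict on effectiveness.

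**The concern.** A two-sided test answers whether two means differ. A claim of effectiveness also needs the difference to be in the favourable direction. Section 2 treats the first as sufficient for the second. Because the null is equality, it is rejected just as readily by a large increase in glucose on BP-rapid as by a large decrease, and the rule attaches the same label to both.

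This is a rule the SAP states itself, and the only one it gives for calling the intervention effective. A pre-specified success criterion should give the right answer when applied exactly as written. This one gives the wrong answer in one tail.

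**Working it through.** **1. Apply the rule to each possible result**

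| Result of the BP-rapid minus UC contrast | Null rejected? | Verdict under Section 2 as written | Verdict with direction required |
|---|---|---|---|
| p<0.05, glucose lower on BP-rapid | Yes | Effective | Effective |
| p<0.05, glucose higher on BP-rapid | Yes | Effective | Not effective; unfavourable |
| p≥0.05 | No | Not shown effective | Not shown effective |

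The two rules differ only in the second row.

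**2. Size when there is no true difference**

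Inputs: level 0.05 (Section 2) and two-sided p-values (Section 5.1). A symmetric two-sided test puts 0.05 / 2 = 0.025 in each tail.

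- As written: P(declared effective) = 0.025 + 0.025 = 0.05, which is the plan's stated level. Of this, 0.025 is for higher glucose on BP-rapid.
- With direction required: P(declared effective) = 0.025, none of it in the wrong direction.

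A simulation of 400,000 null trials (paired t-test, N=36, 35 degrees of freedom, critical t = 2.030) gave 0.0499 for any rejection, 0.0251 with BP-rapid higher and 0.0248 with BP-rapid lower. This confirms the split, which does not depend on the SD.

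**3. Illustration: a true increase of 10 mg/dl on BP-rapid**

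The SAP states no target effect, so the 10 mg/dl is an assumption. Section 3 gives N=36 and an effective SD of 25 mg/dl, but does not say whether that is the SD of the within-person difference. If it is, SD_diff = 25. If it is the SD within one period and the periods are uncorrelated, SD_diff = 25 × √2 = 35.4. I use that range, with 30 between.

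For a paired t-test, the noncentrality is 10 / (SD_diff / √36). The rejection probability in each tail comes from the noncentral t distribution with 35 degrees of freedom:

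| SD_diff (mg/dl) | Noncentrality | P(reject, BP-rapid higher) | P(reject, BP-rapid lower) | P(declared effective), as written | P(declared effective), direction required |
|---|---|---|---|---|---|
| 25 | 10 / 4.17 = 2.40 | 0.6457 | 0.000009 | 0.6457 | 0.000009 |
| 30 | 10 / 5.00 = 2.00 | 0.494 | 0.000047 | 0.494 | 0.000047 |
| 35.4 | 10 / 5.89 = 1.70 | 0.3784 | 0.000152 | 0.3786 | 0.000152 |

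These figures are conditional on a true increase and on the sentence being followed to the letter. They do not suggest that an increase is likely. The paired t-test stands in for the SAP's three-period repeated-measures model.

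**4. Does the hierarchy need a direction too?**

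No. Section 7.1 tests six two-sided hypotheses in a fixed order, each at 0.05, stopping at the first non-significant result. That controls the familywise error rate for hypotheses of no difference whichever way a difference lies. The fault is in the label attached to the first rejection, not in the sequence.

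**The case against.** The strongest reply is that context supplies the direction. Section 4.1 lists mean glucose as an efficacy outcome, Section 4.2.2 lists the high-glucose measures under hyperglycemia, and the participants have type 1 diabetes with HbA1c up to 11%. Nobody would call higher glucose a success, and pairing a two-sided null with an effectiveness statement is common shorthand. The sign will be visible in any case, because summary statistics are tabulated whatever the tests show. The trial is described as a feasibility study with a convenience sample, and the SAP attaches no action to the word *effective*. The protocol, not available here, may state the expected direction. Finally, 2.5% per tail is true of any two-sided 5% test, and becomes a real error only if someone sees a significant rise and still calls it effective.

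Most of this stands, and it is why the point is minor. It does not remove the defect. The sentence specifies when the word applies, and the condition it gives is rejection alone; the word cannot supply the missing half of its own condition. A direction in the protocol would not correct a SAP sentence that states a different rule.

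**Conclusion.** The concern holds, as a minor error in the wording of the decision rule. Section 2 makes rejection of a non-directional null sufficient for effectiveness, and nothing else in the SAP adds a direction. Under no true difference, the rule as written has a 2.5% chance of declaring effectiveness on a higher mean glucose; this rests only on the two-sided 0.05 level. The larger probabilities in the illustration depend on an assumed true increase and an assumed SD of the difference, and should not be read as practical risk. The two-sided test, the 0.05 level, the model and the Section 7.1 sequence are not in question.

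**What to change.** Keep the two-sided test at 0.05 and replace the decision sentence in Section 2 with wording such as:

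> The intervention will be considered effective only if p<0.05 and the estimated contrast from the model that gives the p-value favours BP-rapid (lower mean glucose than UC). A significant difference in the other direction will be reported as unfavourable to BP-rapid.

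Taking the sign from the same contrast as the p-value keeps the rule usable if the Section 6 rank transformation is applied, because significance and direction then come from one analysis. Section 7.1 stays as it is.

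The cost is an edit to one sentence. Participants, data, sample size, models, p-values and the set of hypotheses formally tested do not change. The document is labelled Version 0.4 and records enrollment as still under way, so on its face the edit could be made when the SAP is finalised.
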